### 13.10.3 Central investigations

At treatment failure in the Randomisation Pathway for either arm (continuous or intermittent treatment arms) the following samples should be sent:

- 20ml blood in EDTA to HMDS central laboratory
- 50ml anti-coagulated blood sent to UK CLL Biobank

### **13.11 Post-progression follow-up**

Following treatment failure all participants will be followed up annually for 3 years, until death, or until the end of the study. For those participants who have consented, long-term follow-up survival data will be collected from routine NHS data.

However, for those who have consented, the QoL and Health Economics questionnaires should be completed at all the timepoints detailed in Appendix 4 even if the participant has progressed before reaching this point in treatment.

### **13.12 Deaths**

All deaths must be recorded on the Notification of Death eCRF within 24 hours of notification to the site trial research team.

All deaths should be assessed to determine whether they meet the criteria of a serious adverse event (SAE), serious adverse reaction (SAR) or suspected unexpected serious adverse reaction (SUSAR). Definitions and reporting requirements for SAEs, SARs and SUSARs can be found in Section 14.

### **13.13 Long term follow up**

For participants who have consented long term survival data will be collected by the CTRU via one off data download of routine data from NHS digital or other central UK NHS bodies. This data will be collected 6 years after the main trial has ended.

### **13.14 Participant withdrawal**

The PI or delegate should ensure that the specific wishes of any participant who wishes to withdraw consent for further involvement in the trial, be that from further treatment and/or follow-up data collection, are defined and documented using the Withdrawal eCRF in order that the correct processes are followed by the CTRU and site following the withdrawal of consent.

Where the participant withdraws consent for further data collection, data collected prior to withdrawal of consent will be included in the analysis. It should be made clear to any participant specifically withdrawing consent for further data collection in a CTIMP that data pertaining to safety will continue to be collected for regulatory reporting purposes and will be included in any safety analysis. In addition it is suggested that the participant is made aware of the fact that if any significant new information becomes available in regard to the treatment they have received in the trial it may be necessary to contact them in the future.

If it is the decision of the PI to withdraw the participant from further involvement in the trial then this should also be documented on the Withdrawal eCRF.

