### 8.1 Overall design and plan of the study

The 'Randomisation Pathway' is designed as a prospective, multicentre, open-label, randomised, controlled, 2-arm, parallel-group, non-inferiority study to compare an intermittent treatment strategy (experimental arm) with continuous treatment (control arm) with ibrutinib for patients with CLL who have responded well to treatment with ibrutinib. The primary outcome for this pathway will be time to treatment strategy failure, defined as the first documented instance of active disease as defined by the 2018 iwCLL criteria (Appendix 1) that does not respond to treatment, or death from any cause.

At randomisation previously treated participants will have been receiving ibrutinib as their second- or subsequent-line of therapy for at least the previous 36 months, whilst front-line participants entering from the FLAIR trial will have received 6 years of treatment with ibrutinib. There is no restriction on maximum duration of treatment for the previously treated cohort prior to enrolment. The recruitment period is 6 years, and each participant will be followed up for at least 3 years after randomisation. Participants will receive treatment during the trials 6 year recruitment period and for the 3 years of follow up, meaning that participants will be on the trial for between 3-9 years, depending upon when they enter the trial. 800 patients will be entered into the Randomisation Pathway with the goal of observing 379 treatment failure or death events.

Participants will be randomised to either an intermittent treatment strategy or to continuous therapy. Treatment allocation (1:1) will be by minimisation with a random element incorporating the following three factors: centre, whether or not the participant was previously treated in FLAIR and minimal residual disease (MRD) level at randomisation.

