### **13.9 Follow up after early treatment discontinuation (prior to treatment failure)**

QoL and Health Economic questionnaires should continue to be completed at the timepoints detailed in Appendix 4.

If a participant explicitly states they do not wish to attend further visits or contribute further data to the study the CTRU should be informed using the Withdrawal eCRF (see Section 13.13).

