## 17.4 Derivation of Endpoints

### 17.4.1 Time to Treatment Strategy Failure

Time to treatment strategy failure is defined as the time from randomisation to time of treatment strategy failure. Treatment strategy failure is defined as the first documented instance of active disease that does not respond to treatment, or death from any cause. If a participant reaches active disease whilst on a break and they continue to meet this criteria whilst on subsequent ibrutinib treatment, then the time of the event is when they first met the criteria for active disease. Individuals who are lost to follow-up, withdraw from all follow-up or continuing with their treatment strategy at the time of analysis will be censored at the date of last assessment. Participants who transfer to an alternate BTK inhibitor without experiencing active disease will be censored at their last assessment pre-transfer.

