## 19.1 General considerations

Statistical analysis is the responsibility of the CTRU statisticians, with the exception of the analysis for cost-effectiveness, which will be undertaken by the Health Economists at the University of Leeds. A full statistical analysis plan will be written before any analysis is undertaken.

For analyses carried out by the CTRU, the analysis plan will be written in accordance with current the CTRU standard operating procedures and will be finalised and agreed by the following people: the trial statistician and supervising statistician, the Chief Investigator and the CTRU Scientific and Project Delivery Leads. Any changes to the finalised analysis plan, and reasons for changes, will be documented.

The analysis population used will depend on the pathway and is detailed below. The intention to treat (ITT) population will include participants according to their randomisation allocation, regardless of eligibility and whether they prematurely discontinued treatment or did not comply with the regimen. The per-protocol (PP) population will exclude individuals who did not uptake their trial treatment or strategy, as well as those who are found to be ineligible following randomisation or any other major protocol violations, as determined by the CI. The safety population will consist of all participants who receive at least one dose of the study treatment on study. The populations for each pathway will be fully defined within the statistical analysis plan (SAP).

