## 19.3 Primary Endpoint Analysis

The primary endpoint will be assessed on both the PP and the ITT population in the Randomisation Pathway, as recommended (21). In order to reject the null hypothesis that the intermittent strategy is

inferior, we require demonstration of non-inferiority in both the PP and ITT populations. If the results of the analyses are discrepant this will be reported to highlight the inconclusiveness result.

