### **19.3.1 Time to Treatment Strategy Failure**

Cox regression analysis will be used to analyse the time to strategy failure accounting for stratification factors (excluding centre), and Kaplan-Meier curves will be presented. The proportional hazards assumptions will be assessed by plotting the hazards over time (i.e., the log cumulative hazard plot). Participants not known to have experienced treatment failure or death at the time of the analysis will be censored at the last date they were known to be alive and not suffering active disease. This comparison will be made against a 2.35% significance level, adjusted to maintain an overall one-sided 2.5% significance level with the included interim analysis of this endpoint. Comparisons will be made against a hazard ratio non-inferiority margin of 1.33, considering the continuous treatment strategy as the reference.

A formal interim analysis on the primary endpoint will be presented to the DMEC when half the number of events (190) have been reported across both treatment arms, with an O'Brien Fleming adjustment used to maintain the overall type I error rate. This is anticipated to be after 5 years of recruitment.

If the upper 95% CI for the observed interim HR is less than the lower bound of our NI margin CI, the trial will be stopped for futility and all participants who are having a treatment break will be able to go back onto therapy. If the lower limit of the 99.5% CI for the HR is higher than the upper bound of our NI margin CI, the trial will be able to report early evidence of non-inferiority. This confidence level corresponds to a significance level of 0.25% for a one-sided test. This value has been calculated using the alpha spending approach with the O'Brien Fleming approximation (22).

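### Section 13.14 does not limit a PI-decided withdrawal to trial treatment, so primary-endpoint follow-up can end without the participant asking and later failures would be censored

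*Protocol*

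**What the plan says.** Section 13.14 has two routes. The first is the participant's own wish to withdraw, "be that from further treatment and/or follow-up data collection". The second begins "If it is the decision of the PI to withdraw the participant from further involvement in the trial" and then requires only that the decision be entered on the Withdrawal eCRF. The second route repeats the phrase that the first has just explained. It gives no grounds, no review by the CTRU or Chief Investigator, and no instruction to go on collecting failure and death data.

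Other sections treat follow-up differently:

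- 13.17 has participants followed until death or the final analysis.
- 13.9 ends visits and data only in this case: "If a participant explicitly states they do not wish to attend further visits or contribute further data to the study".
- 13.15.2 keeps follow-up going even after transfer to a non-participating site, unless the participant does not want it.
- 12.2 lets repeated non-compliance lead to withdrawal from study treatment, not from follow-up.
- 14.5 keeps participants who are off treatment in follow-up unless they are unwilling, but says so only for pregnancy.

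On analysis, 17.4.1 states: "Individuals who are lost to follow-up, withdraw from all follow-up or continuing with their treatment strategy at the time of analysis will be censored". Section 19.3.1 adds: "Participants not known to have experienced treatment failure or death at the time of the analysis will be censored". Neither asks who decided the withdrawal. Section 19.1 analyses participants as randomised, "regardless of eligibility and whether they prematurely discontinued treatment or did not comply with the regimen", and 19.3 states: "we require demonstration of non-inferiority in both the PP and ITT populations".

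**The concern.** The trial is a "prospective, multicentre, open-label, randomised, controlled, 2-arm, parallel-group, non-inferiority study", and the local clinician assesses disease (section 16). The PI therefore knows both the arm and the clinical course. If the PI's decision ends follow-up, the resulting censoring may depend on prognosis, which the Cox analysis assumes it does not.

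Requiring non-inferiority in both populations gives no protection, because an event that was never collected is missing from both. The long-term NHS download in 13.13 does not repair this: it covers survival only, for consenting participants, 6 years after the main trial ends.

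One situation is particular to the pausing arm. Under 8.1 and 13.8, active disease found during a pause becomes a failure only if it is still present at the next follow-up after ibrutinib is resumed. A withdrawal from follow-up between those visits leaves no event. Section 12.5 has no such waiting period for the continuous arm.

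**Working it through.** **1. Do the sections agree on who can end follow-up?** Under 13.9 and 13.15.2 the participant's wish ends it. Under 13.17 it runs to death or the final analysis. Under 13.14 a PI decision may end it, because the wording includes data collection and nothing narrows it. Section 13.14 is the one out of line. Section 13.9 does not fill the gap: after early discontinuation it expressly continues only the quality-of-life and health-economic questionnaires, not disease assessment.

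**2. What is lost?** A failure documented before withdrawal stays in the analysis. After withdrawal, 17.4.1 censors at the last assessment and 19.3.1 at the last date known alive without active disease. Later failures, and pausing-arm active disease not yet confirmed, are not counted.

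**3. The plan's own figure (18.1).** Inputs: margin 1.33, one-sided 2.5%, 80% power, 1:1 allocation. Events = 4(1.960 + 0.842)² / (ln margin)².

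- At 1.33: 386.0, rounded up to 387, which is 2.1% above the stated 379.
- At an unrounded margin of 4/3: 379.4.

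So 379 is reproduced. The 45%/55% mixture of 10-year and 4-year medians also solves to 5.84 years, as stated.

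**4. Illustrative worst case.** Assume a true hazard ratio of exactly 1.33, so that any non-inferiority claim is false. Assume a fraction f of pausing-arm failures is censored at the moment of failure and none in the continuous arm. The protocol gives no value for f.

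- Observed hazard ratio: h = 1.33(1 − f).
- Pausing-arm events: 379·h/(1 + h); the rest are continuous-arm events.
- SE = √(1/pausing events + 1/continuous events).
- One-sided error = Φ(−ln(1 − f)/SE − 1.960).

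For f = 2%: h = 1.303, events 214.5 and 164.5, SE = 0.1036, so Φ(0.195 − 1.960) = 3.9%.

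For f = 5%: h = 1.264, events 211.6 and 167.4, SE = 0.1034, so Φ(0.496 − 1.960) = 7.2%.

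| f | failures lost (approx.) | formula | Cox simulation, 8,000 runs |
|---|---|---|---|
| 0 | 0 | 2.5% | 2.7% |
| 1% | 2 | 3.1% | not run |
| 2% | 4 | 3.9% | 4.2% |
| 3% | 6–7 | 4.8% | not run |
| 5% | 11 | 7.2% | 7.2% |
| 10% | 22–23 | 17.4% | 17.7% |

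The 8,000-run simulation used 400 per arm, uniform 6-year accrual, an exponential control arm with median 5.84 years, and analysis at the 379th event. Its standard error at f = 0 is √(0.025 × 0.975/8000) = 0.17 points. A second simulation, with 4,000 runs per setting, the 45/55 mixture and a stratified Cox model, gave 2.8%, 4.1% and 7.2% at f = 0, 2% and 5%, with mean hazard ratios of 1.30 and 1.26 for the last two. At the final-look level of 2.35% in 19.3.1, the formula gives 3.7% and 6.8% for 2% and 5%.

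**5. The opposite direction.** Assume a true hazard ratio of 1 and a fraction f of continuous-arm failures censored. The observed hazard ratio is 1/(1 − f), and power = Φ((ln 1.33 + ln(1 − f))·√379/2 − 1.960). This gives 79.3% at f = 0, 73.2% at 2% and 62.4% at 5%. Here the loss is in power, not in type I error.

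**The case against.** The sentence is mainly a documentation rule. It does not say that follow-up ends, and a PI decision could be for treatment only. Section 13.17 makes follow-up the default, 13.12 requires deaths notified to the site to be recorded, and 12.2, 12.4 and 12.5 give routes for non-compliance, stopping early and treatment failure that do not end data collection. All of this stands, and it makes heavy use of the PI route unlikely. None of it limits the route, however, and a site can use it as written.

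A reader might infer that failures can be removed from the ITT analysis at the PI's discretion. The documents do not support that: 19.1 keeps every randomised participant in their arm, and 17.4.1 deletes no documented failure. What can be lost is an event not yet observed or not yet confirmed.

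A reader might also take 4% or 7% as the trial's expected error rate, or conclude that the bias favours the pausing arm. Neither follows. The figures assume losses in one arm only, timed exactly at failure. That two simulations and a formula agree confirms the arithmetic, not the scenario. The pausing-arm confirmation window is a real difference between the arms, but nothing in the protocol says that PIs would withdraw participants in it.

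The SAP is not shown and may well report withdrawals by arm and include sensitivity analyses for censoring. It cannot recover outcomes that sites were allowed to stop collecting.

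**Conclusion.** The point holds as a gap in wording with a possible statistical consequence. Section 13.14 leaves the PI's decision open to include follow-up, out of line with the rest of the protocol, and the censoring rules then apply whoever decided. The result is potential informative censoring of later or unconfirmed failures in both ITT and PP.

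Its size cannot be estimated, because the protocol gives neither the frequency nor the direction of PI withdrawals. The worst case in one direction is a one-sided error of about 4% if 2% of pausing-arm failures are lost, and about 7% if 5% are lost. In the other direction the cost is power. The 5% dropout allowance in 18.1 protects the sample size, not the test, against selective loss. No sample-size figure changes. This is a cheap improvement worth making, not a demonstrated bias.

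**What to change.** In 13.14, state that a PI decision withdraws the participant from trial treatment only. State also that follow-up for active disease, next treatment and death continues unless the participant withdraws consent for data collection. Align 13.9 and 17.4.1 with this, so that 13.9 names disease and survival follow-up as well as questionnaires. On the Withdrawal eCRF, record who decided (PI or participant) and the scope (treatment, or data collection), so that the two can be reported by arm.

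The cost is one or two sentences, an eCRF field if the form does not already hold this, and a few more routine follow-up records. The grounds for stopping treatment are unaffected. With follow-up kept, f in the calculation above is zero for PI-decided withdrawals and the test returns to its nominal level.

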### **13.15 Participant transfer**

If a participant is being transferred to a different site, the Participant Transfer eCRF must be completed.

### **13.15.1 Transfer to another site participating in STATIC**

Copies of any paper CRFs, Informed Consent Documents and any other relevant correspondence are sent to the new hospital, with originals kept at the original site. Data from before the date of transfer is questioned with the original site, data after the transfer date is questioned with the new site. Both sites must ensure that the participant transfer is recorded on the participant log in the Investigator Site File and the Pharmacy Site File

### **13.15.2 Transfer to a site that is NOT participating in STATIC**

- All trial treatment will cease. Any further treatment for CLL received by the participant will be off-study.
- If the participant agrees to be followed up at the new site, it is the responsibility of the original site to gather follow up data from the new site in order to complete the eCRFs. The original site will keep all trial documentation and ensure that the participant transfer is recorded on the participant log in the Investigator Site File and the Pharmacy Site File.
- If the participant does not want to be followed up at the new site, a Participant Withdrawal eCRF must be completed by the original site.

## **13.16 Protocol violations**

A protocol violation can be defined as: any accidental or unintentional change to, or non-compliance with the protocol that **does** increase risk or decrease benefit, or has a significant effect on the participant's rights, safety, or welfare, or on the integrity of the data.

Examples of a violation include, but are not restricted to:

- Failure to obtain valid informed consent prior to performing any other trial investigation or procedure
- Breaches of eligibility criteria
- Drug administration errors relating to the IMP (e.g. overdose, underdose, not performing specified suitability for treatment tests, not modifying dose in line with required modifications)
- Non-adherence to the protocol in relation to prohibited concomitant therapy whilst receiving trial treatment.
- Concomitant medication

During the COVID-19 pandemic, sites may have local policies in place to limit hospital visits or to allow for temporary limitations on resources/facilities. If a protocol violation has occurred due to COVID-19-related reasons, sites are still required to follow the guidance in this section and to report the violation as per normal processes.

Protocol violations should be reported immediately to the CTRU using the Protocol Violations eCRF. Protocol violations will be monitored and escalated to the Trial Management Group (TMG) for review of medical significance. Medically significant protocol violations will be considered as to whether they meet the criteria for Serious Breaches of GCP (Section 21.1).

The following events do not need to be reported as a protocol violation as long as the local investigator deems it not medically significant and the event does not result in an SAE/SUSAR:

- A rescheduled study visit

- Participant refusal to complete scheduled research activities
- Limited dosing errors by participant, i.e. 14 missed doses over 2 weeks, that did not result in an SAE and that were deemed not medically significant by site. (NB: Where 15 or more doses are missed the event must be reported as a protocol violation).

### **13.17 Definition of end of trial**

The end of the trial is defined as the date of the collection of the last participant's last data item. Participants will be followed up until death or until the final analysis as described in Section 19 (whichever is sooner).

### **13.18 Site and Trial Closure**

The CTRU will notify sites of procedures for site closure following the trial final analysis.

# 14 PHARMACOVIGILANCE PROCEDURES

## 14.1 General definitions

The standard definitions are derived from the document 2011/C 172/01 ‘Detailed guidance on the collection, verification and presentation of adverse event/reaction reports arising from clinical trials on medicinal products for human use (“CT-3”)’ (based on the Clinical Trials Directive 2001/20/EC) and from the CIOMS Working Group VII definitions.

Term	Definition
Adverse Event (AE)	
Any untoward medical occurrence in a patient or clinical trial subject administered a medicinal product and which does not necessarily have a causal relationship with this treatment.
 
An adverse event can therefore be any unfavourable and unintended sign (including an abnormal laboratory finding, for example), symptom or disease temporally associated with the use of a medicinal product, whether or not considered related to the medicinal product.

Adverse Event of Special Interest (AESI)	
An adverse event of special interest (serious or non-serious) is one of scientific and medical concern specific to ibrutinib, for which ongoing monitoring and rapid communication by the investigator to the sponsor could be appropriate. Such an adverse event might require further investigation in order to characterise and understand it. Depending on the nature of the adverse event, rapid communication by the trial sponsor to other parties (e.g. regulators) might also be warranted.

Adverse Reaction (AR)	
All untoward and unintended responses to an IMP related to any dose administered.
 
This definition covers also medication errors and uses outside what is foreseen in the protocol, including misuse and abuse of the product.
 
This definition implies a reasonable possibility of a causal relationship between the event and the IMP. This means there are facts (evidence) or arguments to suggest a causal relationship.

Serious Adverse Event (SAE)	
Any untoward medical occurrence or effect that at any dose:
 
 
• Results in death,
 
• Is life-threatening,
 
• Requires hospitalisation or prolongation of existing hospitalisation,
 
• Results in persistent or significant disability or incapacity,
 
• Results in a congenital anomaly or birth defect,
 
• Jeopardises the subject or may require an intervention to prevent one of the above characteristics/consequences – herein referred to as ‘Other important medical events’
 
 
These characteristics/consequences have to be considered at the time of the event. For example, regarding a life-threatening event, this refers to an event in which the subject was at risk of death at the time of the event; it does not refer to an event which hypothetically might have caused death if it were more severe.

	Medical and scientific judgement must be exercised in deciding whether an event is “serious” in accordance with these criteria.
Serious Adverse Reaction (SAR)	Reference is made to the criterion of “Seriousness” above in relation to SAE and the definition of AR. Any suspected transmission via a medicinal product of an infectious agent is also considered a serious adverse reaction.
Suspected Unexpected Serious Adverse Reaction (SUSAR)	An adverse reaction, the nature or severity of which is not consistent with the applicable Reference Safety Information (Section 14.2). The term “severity” is used here to describe the intensity of a specific event. This has to be distinguished from the term “serious”. Reports which add significant information on the specificity, increase of occurrence, or severity of a known, already documented serious adverse reaction constitute unexpected events.

